Rationale: Posaconazole is indicated for prophylaxis of invasive aspergillosis and can also be used as treatment of several fungal infections. Therapeutic Drug Monitoring (TDM) of posaconazole can be performed to maintain efficacy, since exposure-respons relationships are described for posaconazole (ref Dolton AAC 2012: mail [name]). Recently was shown that the plasma concentration of another antifungal agent, voriconazole, is influenced by inflammation, measured by C-reactive protein value [van Wanrooy et al AAC 2014, Encalada Ventura et al AAC 2015; manuscript in preparation of study with clinical trials gov identifier NCT02074462]. During severe inflammation the metabolism of voriconazole is reduced via downregulation of cytochrome P450 enzymes, which results in high voriconazole plasma concentrations. Subsequently, dosages can be adjusted to avoid toxicity. However, if the degree of inflammation decreases again, the metabolism of the drug increases with as a result possible subtherapeutic drug concentrations. As posaconazole is only metabolized in limited extend by cytochrome P450 enzymes it is likely that posaconazole is not influenced by inflammation. However, no published data is available to support the hypothesis that exposure of posaconazole is not influenced by inflammation. Data on stable posaconazole exposure during treatment will result in a clinical benefit over voriconazole.

Objective: The objective of this study proposal is to determine if posaconazole drug exposure is influenced during different stages of inflammation.

Study design: A prospective observational study will be performed at the University Medical Center Groningen, the Netherlands to determine if posaconazole drug exposure is influenced by inflammation.

Study population: patients receiving posaconazole for treatment or (secondary) prophylaxis of fungal infections

Intervention (if applicable): none

Main study parameters/endpoints: Main study parameter is the posaconazole drug exposure during different stages of inflammation. Subsequently, a multiple linear regression model that describes the contribution of inflammation on posaconazole levels will be developed. At last, the relation between the change in CRP and change in drug plasma concentration from this study will be compared with the results of our earlier prospective voriconazole study [NCT02074462] based on matched patients.

Nature and extent of the burden and risks associated with participation, benefit and group relatedness: no risk or burden for the patients as samples from routine patient care

are used. Future patients may benefit from the results of this study, as more insight is given in the pharmacokinetics of posaconazole.

1. INTRODUCTION AND RATIONALE

Invasive aspergillosis (IA) is the leading cause of infection-related death in patients with acute leukemia and in hematopoietic stem cell transplant (HSCT) recipients. Various pathophysiological changes in severely ill patients, such as cancer patients, can affect the pharmacokinetics of antimicrobial agents. Adequate posaconazole drug exposure is associated with better treatment outcome. Until recently, posaconazole drug absorption was compromised by drug-drug interactions and insufficient food intake. This resulted in substantial intra- and interindividual patient variability in the pharmacokinetics of posaconazole [Dolton *et al* AAC 2014, Brüggemann *et al* CID 2009, Alffenaar *et al* CID 2009, Dolton *et al* AAC 2012, Vaes *et al* AAC 2012, Tonini *et al* AAC 2012]. The introduction of the new oral formulation and intravenous preparation improved drug exposure. [Maertens *et al* AAC 2014, Kraft *et al* AAC 2014].

For voriconazole it was recently shown by our group that metabolism of voriconazole was influenced by severe inflammation, measured by C-reactive protein value [van Wanrooy *et al* AAC 2014, Encalada Ventura *et al* AAC 2015; manuscript in preparation of study with clinical trials.gov identifier NCT02074462]. The underlying mechanism was cytokine induced down regulation of cytochrome P450 expression. The reduced metabolism resulted in voriconazole plasma concentrations exceeding the therapeutic window of voriconazole posing the patient at risk for toxicity. Subsequently, dosages were adjusted to remain the voriconazole plasma concentration within the therapeutic window. However, when the degree of inflammation decreased and thereby the metabolism of voriconazole increased, patients were at risk for subtherapeutic drug concentrations. Therefore, it was concluded that inflammation should be taken into account when therapeutic drug monitoring of voriconazole is performed.

As posaconazole is only metabolized in limited extend by cytochrome P450 enzymes it is likely that posaconazole is not influenced by inflammation. However, no published data is available to support the hypothesis that exposure of posaconazole is not influenced by inflammation. Data on stable posaconazole exposure during treatment will result in a clinical benefit over voriconazole.

2. OBJECTIVES

Primary Objective:

The objective of this study proposal is to explore the posaconazole drug exposure during treatment in different stages of inflammation.

Secondary Objective(s):

The secondary objective is to develop a multiple linear regression model to describe the contribution of inflammation to the variability in posaconazole concentration. Subsequently, the relation between change in CRP and change in drug plasma concentration from this

study will be compared with the results of our earlier prospective voriconazole study [NCT02074462] based on matched patients.

3. STUDY DESIGN

A prospective observational study will be performed at the University Medical Center Groningen, the Netherlands using longitudinal data collection to develop a dosing algorithm based on data of inflammatory markers and posaconazole concentrations.

4. STUDY POPULATION

4.1 Population (base)

Patients that receive posaconazole for treatment or (secondary) prophylaxis of fungal infections

4.2 Inclusion criteria

In order to be eligible to participate in this study, a subject must meet all of the following criteria:

-aged ≥ 18 yrs -receive posaconazole -written informed consent

4.3 Exclusion criteria

A potential subject who meets any of the following criteria will be excluded from participation in this study:

-concomitantly using a strong inhibitor or inducer of CYP P450

4.4 Sample size calculation

To be able to develop and validate a model based on inflammatory markers and posaconazole multiple data points are mandatory. We estimate that it is feasible to collect 3-4 data points per treatment week.

Taken into account the non-invasive nature of this study, the routine sampling of critically ill patients we plan to recruit 30 patients for this study.

5. TREATMENT OF SUBJECTS

Subjects receive posaconazole as standard treatment or (secondary) prophylaxis for fungal infection. As the treatment with posaconazole and TDM are part of routine care they are neither initiated nor altered for study purposes (no intervention). Therefore this study is not being subjected to Medical Research Involving Human Subjects Act. Only data of standard care and TDM will be collected to develop the dosing algorithm for posaconazole during severe inflammation.

Attending physicians are allowed to request drug concentration measurement for patient care. If the posaconazole concentration is low the attending hospital pharmacist will provide the attending physician with a dosage advice. Dosages will be increased if levels are too low or decreased if levels are too high. The increase or decrease of the dosage will be based on the measured concentration, initial dosage and patient characteristics. Follow up will be performed to assure that the level reaches and remains in the therapeutic window.

5.1 Investigational product/treatment

Not applicable

5.2 Use of co-intervention (if applicable)

Not applicable

5.3 Escape medication (if applicable)

Not applicable

6. INVESTIGATIONAL PRODUCT

Not applicable; subject receive posaconazole as standard treatment or (secondary) prophylaxis for fungal infection

6.1 Name and description of investigational product(s)

Noxafil 100mg Tablet; Noxafil 300mg concentrate for solution for infusion; Noxafil 40 mg/mL oral suspension

6.2 Summary of findings from non-clinical studies

See SmPC of Noxafil

6.3 Summary of findings from clinical studies

See SmPC of Noxafil

6.4 Summary of known and potential risks and benefits

Non due to the nature of this study

6.5 Description and justification of route of administration and dosage

Depending on choice of attending physician; IV or PO

6.6 Dosages, dosage modifications and method of administration

Depending on choice of attending physician, dosage modifications based on measured posaconazole concentrations are part of routine care.

6.7 Preparation and labelling of Investigational Medicinal Product

Not applicable

6.8 Drug accountability

Not applicable because Noxafil is not considered a study drug. Data on administration of the drug will be collected from the medical chart.

7. NON-INVESTIGATIONAL PRODUCT

Not applicable

7.1 Name and description of non-investigational product(s)

Not applicable

7.2 Summary of findings from non-clinical studies

Not applicable

7.3 Summary of findings from clinical studies

Not applicable

7.4 Summary of known and potential risks and benefits

Not applicable

7.5 Description and justification of route of administration and dosage

Not applicable

7.6 Dosages, dosage modifications and method of administration

Not applicable

7.7 Preparation and labelling of Non Investigational Medicinal Product

Not applicable

7.8 Drug accountability

Not applicable

8. METHODS

8.1 Study parameters/endpoints

8.1.1 Main study parameter/endpoint

Explore the posaconazole drug exposure during treatment in different stages of inflammation.

8.1.2 Secondary study parameters/endpoints (if applicable)

Develop a multiple linear regression model that describes the contribution of inflammation on posaconazole levels. Compare the relation between change in CRP

and change in drug plasma concentration from this study with the results of our earlier prospective voriconazole study [NCT02074462] based on matched patients drug plasma concentration from this study will be compared with the results of our earlier prospective voriconazole study [NCT02074462] based on matched patients.

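### The voriconazole comparison is defined on change in concentration without dose correction, although doses of both drugs follow concentration; under the protocol's own hypothesis this overstates the contrast by roughly 10–30% on the log scale

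*Combined protocol and SAP*

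**What the plan says.** The comparison appears three times, each time without a dose term.

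- Summary, main study parameters: "the relation between the change in CRP and change in drug plasma concentration from this study will be compared with the results" of the voriconazole study.
- Section 2, secondary objective: "Subsequently, the relation between change in CRP and change in drug plasma concentration from this" study is to be set against that study.
- Section 8.1.2: "and change in drug plasma concentration from this study with the results of our earlier prospective voriconazole study".

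All three name matched patients as the basis. None gives the matching variables, the interval over which change is taken, or the scale.

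The protocol also describes dosing guided by concentration for both drugs.

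- Voriconazole, section 1: "The reduced metabolism resulted in voriconazole plasma concentrations exceeding the therapeutic window of voriconazole", and then "Subsequently, dosages were adjusted to remain the voriconazole plasma concentration within the therapeutic window".
- Posaconazole, section 5: "Dosages will be increased if levels are too low or decreased if levels are too high". Section 6.6 confirms that such changes are routine care.

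Section 10.2 adjusts for posaconazole dose and route, but in a mixed model of posaconazole concentrations only. Section 10 gives no method for the cross-drug comparison. The group tests that open section 10 concern patient characteristics, and section 10.3 is marked not applicable.

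**The concern.** When dose is changed because of the measured level, a later change in concentration has two sources: the change in CRP and the change in dose. For a drug whose level rises with inflammation the two are linked in time. High CRP raises the level, the dose is cut, CRP then falls, and the level drops for both reasons. A slope of concentration change on CRP change credits the whole drop to CRP.

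Matching on characteristics at the start of treatment does not address this, because the dose changes happen during follow-up.

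This is the only planned comparison between the drugs, and the Summary and section 1 look to it for a clinical benefit of posaconazole over voriconazole. What is at stake is the size of that contrast. The posaconazole model of section 10.2 is not in question.

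**Working it through.** **Inputs from the documents.** 30 patients and 3–4 samples per treatment week (section 4.4); dose changes driven by concentration (sections 1, 5 and 6.6); the protocol's hypothesis that voriconazole is affected and posaconazole is not. The documents give no slopes, SDs or dose-change frequencies, so there is no planned figure to reproduce and every other input below is an assumption. Relative dose steps are simulation inputs, not proposals.

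**Step 1: the algebra.** Suppose concentration C is proportional to dose D. For one interval, with x = (change in CRP)/100:

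change in log C = βx + change in log D + error.

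The least-squares slope through the origin is then

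b = β + Σ(x · change in log D) / Σx².

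The second term is the bias. It is positive when doses are cut as CRP falls. Replacing log C by log(C/D) removes it.

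**Step 2: size by hand.** A dose cut of one third is a log change of ln(2/3) = −0.41. Let CRP fall by 100 mg/L in everyone (x = −1), and let 10% or 20% of patients carry such a cut at the end of the interval. The bias is 0.10 × 0.41 = 0.041 or 0.20 × 0.41 = 0.082. Against a true slope of 0.26 (a 30% rise per 100 mg/L, since ln 1.30 = 0.26), that is 16% or 32%.

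**Step 3: simulation with identical, symmetric titration for both drugs.** Assumed: CRP about 150 mg/L at the start, halving weekly; 10 samples 2 days apart; a window centred on the zero-CRP median with 10% or 20% of levels outside each limit; relative dose steps of 20% or 40%.

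| Log slope per 100 mg/L CRP | True | Without dose correction | Dose-normalised |
|---|---|---|---|
| Affected drug, within-patient slope | 0.26 | 0.30–0.34 | true slope recovered |
| Affected drug, within-patient slope | 0.40 | 0.47–0.50 | true slope recovered |
| Unaffected drug | 0 | about 0 | about 0 |

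From the first row, 0.30/0.26 = 1.15 and 0.34/0.26 = 1.31. First-to-last change with a fitted intercept gave an inflation of 11–19%. Change between consecutive samples also inflated the affected drug's slope, to as much as 0.34 against 0.26.

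**Step 4: a second set of settings.** A separate run used the same two-sided window for both drugs (10% high, 10% low), with voriconazole at +30% per 100 mg/L and posaconazole at 0. The ratio of fold-changes was 1.34–1.43 against a true 1.30. On the log scale, ln 1.34/ln 1.30 = 0.293/0.262 = 1.12 and ln 1.43/ln 1.30 = 0.358/0.262 = 1.36. The posaconazole slope was +0.1 to +1.2%. The true difference was detected in over 99% of simulated studies.

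**Step 5: where the range does not hold.**

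- *Larger.* CRP fell smoothly, the dose changed at every out-of-window level, and typical voriconazole levels lay nearer the upper limit on the log scale. First-to-last change gave 0.66 against 0.40 through the origin (+65%), and 0.57 with an intercept (+43%).
- *Smaller or reversed.* CRP rose in half the patients. First-to-last log slopes were 0.40 and 0.37 against 0.40. On the absolute scale the slope without correction was below the dose-normalised one: 2.20 against 2.96, and 2.83 against 5.30 concentration units per 100 mg/L.

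**The case against.** The best defence is that the protocol names a topic, not an estimator. It nowhere says that uncorrected concentrations will be used, and section 10.2 shows that the authors adjust for dose when they write out a model. That is fair, and the point is therefore conditional. But the only quantity named is change in concentration, and no analysis section supplies the missing correction.

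The results of the earlier study might already be dose-corrected, and section 1 describes dose adjustment across several cited voriconazole sources rather than in that study specifically. Matching might also use dose history. The documents settle neither. If only one side were dose-corrected, the two slopes would still not measure the same thing.

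It also stands that this is a secondary comparison, that a real difference of the assumed size would almost always be found, and that the bias is not always upward.

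A reader might infer something stronger: that titration runs in opposite directions, voriconazole for high levels and posaconazole for low ones, and so creates a drug difference where inflammation affects neither. Section 5 does say "If the posaconazole concentration is low the attending hospital pharmacist will provide the attending physician with a dosage advice". But it goes on to provide for changes both ways, and section 1 adds for voriconazole that "when the degree of inflammation decreased and thereby the metabolism of voriconazole increased, patients were at risk for subtherapeutic drug concentrations". Mainly opposite titration is not established. With the same symmetric window for both drugs and no CRP effect in either, rejection at the 5% level was 4–6%. Even under opposite titration, first-to-last change with an intercept left both slopes within 0.01 of zero. A voriconazole with no CRP effect also contradicts section 1, which attributes its high levels to inflammation. Nor do the documents support saying that dosing always pushes the two slopes apart.

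**Conclusion.** The concern holds in a limited form. As defined, the comparison has no dose correction, while the dosing of both drugs depends on the outcome being compared. If it is carried out that way, with voriconazole affected, posaconazole not, and CRP falling, the voriconazole slope and hence the contrast are overstated. The overstatement is roughly 10–30% on the log scale under the same symmetric titration, and one set of settings reached 36%.

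This does not depend on opposite titration. It does depend on the assumed CRP course, variability, frequency of dose changes and model, on none of which the documents give figures. The direction of the conclusion would probably survive, but the reported size would not be reliable.

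**What to change.** In section 8.1.2 and section 10, define the comparison in the same way for both drugs:

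1. **Outcome:** log(concentration/dose at that sample), adjusted for route and, for posaconazole, for oral formulation, since section 6.1 lists both tablet and suspension. As a sensitivity analysis, use log concentration with log dose as a covariate.
2. **Estimate:** a drug-by-CRP interaction in a mixed model with patient random effects and serial correlation. Alternatively, compare the two studies' dose-corrected log slopes using their standard errors. Report the ratio of fold-changes per stated CRP increment with its 95% CI.
3. **Reporting:** the number and direction of dose changes for each drug, the matching variables, and the interval over which change is taken.
4. **Fallback:** if voriconazole dose per sample is not available, restrict to intervals known to have no dose change where possible. Otherwise label the comparison descriptive and say that it is not dose-corrected. Switching to change between consecutive samples is not a substitute, because it does not remove the bias.

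The cost is SAP wording and modest programming. Section 6.8 already provides for collecting posaconazole administration data. The documents do not say whether the earlier study holds voriconazole dose per sample. Dose normalisation assumes concentrations roughly proportional to dose, which the documents do not establish for either drug, hence the sensitivity analysis. The section 10.2 model needs no change.

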8.1.3 Other study parameters (if applicable)

Not applicable

8.2 Randomisation, blinding and treatment allocation

Not applicable

8.3 Study procedures

-Patients starting on posaconazole treatment will be evaluated for inclusion.

-After informed consent is obtained medical data will be collected from the medical chart and plasma samples from routine analysis will be obtained.

-Samples for posaconazole and inflammatory analysis will be collected 3-4 times weekly during treatment. Inflammatory markers like CRP will be determined by the department of Clinical Chemistry of the UMCG. Other inflammatory markers of IL-6, IL-8 and procalcitonin will not be determined, since these markers are not routinely measured. Posaconazole plasma concentrations (trough levels) will be measured with a validated and externally tested LC-MS/MS method of analysis [Alffenaar *et al* J Chrom B 2009].

8.4 Withdrawal of individual subjects

Subjects can leave the study at any time for any reason if they wish to do so without any consequences.

8.4.1 Specific criteria for withdrawal (if applicable)

Not applicable

8.5 Replacement of individual subjects after withdrawal

Any subject leaving the study will be replaced

- 8.6 Follow-up of subjects withdrawn from treatment Not applicable
- 8.7 Premature termination of the study Not applicable

9. SAFETY REPORTING

Because this study proposal does not consider an investigational drug and the use of posaconazole and TDM are part of routine care, safety reporting is not subjected to the procedures described in the Medical Research Involving Human Subjects Act.

Because the posaconazole is part of routine care safety reporting will be performed according to Dutch Law ('Geneesmiddelenwet' in English: Medication Act) to the The Netherlands Pharmacovigilance Centre Lareb.

9.1 Section 10 WMO event

Not applicable

9.2 AEs, SAEs and SUSARs

9.2.1 Adverse events (AEs)

Reporting according to Dutch Law.

9.2.2 Serious adverse events (SAEs)

Reporting according to Dutch Law.

9.2.3 Suspected unexpected serious adverse reactions (SUSARs)

Reporting according to Dutch Law.

9.3 Annual safety report

Not applicable, only for investigational drugs

9.4 Follow-up of adverse events

Will be performed in routine patient care

9.5 Data Safety Monitoring Board (DSMB) / Safety Committee Not applicable

10. STATISTICAL ANALYSIS

Descriptive analysis

The Mann-Whitney U test (continuous data) and the Fisher's exact test (binominal data) were used to assess possible differences between the patients, in terms of demographics, underlying disease, VCZ treatment, laboratory parameters and co-medication.

10.1 Descriptive statistics

Demographic characteristics of the patients will be described. Numerical variables will be summarized with medians and interquartile range and categorical variables as frequencies and percentages.

10.2 Longitudinal data analysis

The longitudinal data of the posaconazole concentration will be analyzed with a linear mixed model. A log transformation will be performed if the data are not normally distributed. A random additive effect will be selected for patients to address different concentrations between patients. A first-order autoregressive correlation between posaconazole trough concentrations over time will also be selected to correct for differences in intervals between observations. To investigate the effect of inflammation on posaconazole concentration, the Wald type III test will be conducted after correcting for gender, age, posaconazole dose and route of administration, liver enzymes (ALP, ALAT, ASAT, γ -GT and total bilirubin) and the use of interacting co-medication. The analysis will be performed using SAS 9.3 (SAS Institute Inc., Cary, NC, USA). A p value < 0,05 is considered statistically significant.

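### Section 10.2 does not separate a patient's average inflammation from that patient's changes over time, so its inflammation effect mixes within- and between-patient associations

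*Combined protocol and SAP*

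**What the plan says.** Section 10.2 of the combined protocol and SAP gives the model: "The longitudinal data of the posaconazole concentration will be analyzed with a linear mixed model". The patient effect is a random intercept: "A random additive effect will be selected for patients to address different concentrations between patients". On the errors it says: "A first-order autoregressive correlation between posaconazole trough concentrations over time will also be selected". On the test it says: "To investigate the effect of inflammation on posaconazole concentration, the Wald type III test will be conducted", and this is done "after correcting for gender, age, posaconazole dose and route of administration, liver enzymes", total bilirubin and interacting co-medication. The significance rule is "A p value < 0,05 is considered statistically significant".

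Section 10.2 does not name CRP as the model term. It does not say whether inflammation enters as a continuous variable or as stages, and it has no term for a patient's average level. Section 8.3 makes CRP the only inflammatory marker it names for measurement.

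On the question itself, the primary objective in section 2 is broad: exposure across stages of inflammation. The secondary objective includes "the relation between change in CRP and change in drug plasma concentration from this" study, to be set against an earlier voriconazole study. The Summary (Rationale) describes a movement within one patient. Of voriconazole it says that "if the degree of inflammation decreases again, the metabolism of the drug increases".

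**The concern.** A random intercept lets patients differ in level, but it assumes that a patient's level is unrelated to that patient's average CRP. If the two are related, the coefficient of a time-varying covariate is a weighted mix of two slopes: how the concentration moves when one patient's CRP moves, and how patients with high average CRP differ from those with low average CRP. A multi-level stage factor has the same problem.

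The documents make such a relation plausible. Section 4.1 pools treatment and prophylaxis. Section 6.1 lists tablet, infusion and oral suspension, whereas 10.2 adjusts for dose and route, so tablet and suspension may share one oral category. Section 1 says that absorption suffered from low food intake and interactions, and that newer formulations improved exposure. Indication, underlying disease and severity are not in the model.

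If patients with high average CRP absorb less, the between-patient slope is negative. It then opposes the rise that reduced metabolism would cause within a patient, and the result moves toward the expected finding of no influence. Confounding can also create an effect where none exists.

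**Working it through.** The plan has no figure to reproduce: section 4.4 sets the sample size on feasibility, without an effect size or a variance.

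**Inputs from the documents.** 30 patients (4.4); 3–4 samples per treatment week (4.4, 8.3); random intercept, AR(1) and 0.05 level (10.2; two-sided assumed). Duration is not given.

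**Assumptions.**
- 7 samples per patient (about two weeks at 3.5 per week).
- Log concentration: intercept SD 0.5, residual SD 0.35, residual AR(1) 0.5.
- ln CRP: SD 1.0 between and 0.5 within patients; within-patient CRP either independent over time or autocorrelated at 0.5.
- Confounding γ of −0.2 to −0.4: the slope of the patient's level on average ln CRP that remains after adjustment.

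**Formula.** With known variances and one continuous CRP term, the generalised least squares estimate is β + wγ, where β is the within-patient slope and

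w = I_B / (I_B + I_W), I_B = 29·σ²(CRP between)·A, I_W = 30·tr(V⁻¹C), SE = 1/√(I_B + I_W).

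V = 0.25·J + 0.1225·R (J all ones, R the AR(1) matrix), A = 1′V⁻¹1, and C is the within-patient covariance of ln CRP.

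**Between-patient information.** 1′R⁻¹1 = (7 − 5×0.5)/1.5 = 3. Then 3/0.1225 = 24.49, A = 24.49/(1 + 0.25×24.49) = 24.49/7.12 = 3.44, and I_B = 29×1.0×3.44 = 99.7.

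**Within-patient information.**
- CRP independent (tr R⁻¹ = 11; 1′R⁻²1 = 1.444): 0.25×[11/0.1225 − 0.25×1.444/(0.1225²×7.12)] = 0.25×(89.80 − 3.38) = 21.60; ×30 = 648.1.
- CRP autocorrelated 0.5: 0.25×[7/0.1225 − 0.25×3/(0.1225²×7.12)] = 0.25×(57.14 − 7.02) = 12.53; ×30 = 375.9.

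**Split model.** Using within-patient information only, the independent case gives 30×(0.25/0.1225)×(11 − 1.444/3) = 644.0. The autocorrelated case gives 30×(0.25/0.1225)×6 = 367.3.

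Rejection rate under no within-patient effect = Φ(−1.96 + |wγ|/SE) + Φ(−1.96 − |wγ|/SE).

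| | CRP independent | CRP autocorrelated 0.5 |
|---|---|---|
| w | 99.7/747.8 = 0.133 | 99.7/475.7 = 0.210 |
| SE, single term | 0.037 | 0.046 |
| Type I error, γ = −0.2 | 11% | 15% |
| Type I error, γ = −0.4 | 31% | 45% |
| True 0.15 estimated as | 0.123 to 0.097 | 0.108 to 0.066 |
| SE, split | 1/√644.0 = 0.039 | 1/√367.3 = 0.052 |

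**Sensitivity** (independent / autocorrelated CRP):
- *28 samples (about 8 weeks).* 1′R⁻¹1 = (28 − 13)/1.5 = 10, A = 81.63/21.41 = 3.81, I_B = 110.6, I_W = 2794 / 1656. So w = 0.038 / 0.063, and the type I error is 7–13% / 8–18%.
- *ln CRP SD 0.8 both between and within, 7 samples.* I_B = 29×0.64×3.44 = 63.8, I_W = 2.56×648.1 = 1659 / 2.56×375.9 = 962. So w = 0.037 / 0.062, and the type I error is 6–9% / 7–13%.
- *Intercept variance.* The main figures hold the intercept SD at 0.5. If the confounded part comes on top of it, at γ = −0.4 the variance is 0.25 + 0.16 = 0.41. With autocorrelated CRP, A = 24.49/11.04 = 2.22, I_B = 64.3, I_W = 372.9, w = 0.147, SE = 0.048, and the 45% falls to about 23%.

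**Separate simulation** (REML, random intercept without AR(1), 1,000 runs per setting, 4 to 28 samples, slopes in SD units, intraclass correlations 0.3–0.7). With no within-patient effect and a between-patient slope of 0.3 or 0.5, the single term rejected in 6–60% of runs and the split in 4–7%. With 28 samples and both correlations at 0.5, a true 0.15 against a between slope of −0.3 was estimated as 0.135, with power 97% against 98% for the split. With both slopes at 0.15, 7 samples and correlations of 0.3 (concentration) and 0.7 (CRP), the split lowered power from 39% to 26%.

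**The case against.** A reader might infer more than the documents support on four points.

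- *That 10.2 enters raw CRP with one coefficient.* It does not say so. A stage factor is equally compatible with the text, given the wording of the objectives. What is documented is that no separation is planned. The mixing follows under either coding, but the figures above apply to a continuous term.
- *That the study's question is purely within-patient.* The primary objective is wider, and the first secondary aim, explaining variability in concentration, can include differences between patients. Only the rationale and the change-on-change comparison are clearly within-patient. The between-patient coefficient should therefore be kept and reported.
- *That the 10.2 coefficient spoils the voriconazole comparison.* Sections 2 and 8.1.2 describe a comparison of matched patients. Nothing says that it uses this coefficient, and section 10 gives no method for it.
- *That confounding is uncontrolled.* Section 10.2 adjusts for dose, route, five liver tests and co-medication, and section 4.3 excludes strong CYP inhibitors and inducers. This removes part of the confounding. The upper value of −0.4 is severe: it means exp(−0.4) = 0.67, or 33% lower concentrations per unit of average ln CRP after all adjustment. Masking also needs confounding opposite in sign to the true effect.

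The variances, CRP autocorrelation and follow-up are not in the documents, and plausible values make the distortion small. That objection stands as to size. It does not show that the planned model answers the question of change.

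**Conclusion.** The point holds as a fault of specification that can bias the result. Followed as written, 10.2 gives an inflammation effect that mixes two associations, and a random intercept does not remove the between-patient one. Under the main assumptions the between-patient slope carries 13–21% of the weight. The weight falls to about 4–6% when CRP varies widely within patients or sampling runs to about 8 weeks. Since the protocol states no duration, it cannot rely on the favourable case. The direction of any bias is unknown. The documents do not show that a false finding of stable exposure is likely, only that the planned model does not guard against one. The change should be made before analysis.

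**What to change.** In 10.2, state how CRP enters the model. Replace the undefined inflammation term with two terms: the patient's mean ln CRP, and each sample's ln CRP minus that mean. Use the Wald test and confidence interval of the deviation term to answer whether exposure changes with inflammation, and report the patient-mean coefficient alongside it.

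This takes one or two sentences and two derived variables, with no new data. The standard error rises somewhat (0.046 to 0.052, or 0.037 to 0.039, in the main settings), and some power is lost if the two slopes are in fact equal. The split does not remove confounding that varies over time within a patient, such as the dose changes in response to measured levels described in section 5. The report should say so.
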